11.0 Treatment Evaluation

Note: Formal response evaluation should occur every 2 cycles during treatment, with the first response evaluation occurring at the end of cycle 2. Formal response evaluation should occur every cycle during observation. Objective status should be classified as PD vs. Not PD on cycles when a formal response evaluation does not occur.

11.1 Schedule of evaluations: For the purposes of this study, patients should be reevaluated for progression every 28 days during therapy with lenalidomide and AT-101. Formal response evaluation will occur every 2 cycles, with the first formal response evaluation occurring at the end of cycle 2. However, patients will be evaluated prior to each cycle of therapy to identify individuals who have experienced disease progression. Prior to the first formal response evaluation, baseline on study measurements will be used to determine disease progression (e.g. not cycle by cycle comparisons). Once patients undergo formal response evaluation, the nadir value at either baseline or time of response evaluation will be used for evaluating future disease progression. In addition to a baseline scan, confirmatory scans should also be obtained as needed to document objective response at sites of non-palpable lymphadenopathy or organomegaly as indicated in Section 4 or as needed clinically.

NOTE: Information from CT scans is not considered in the standard classification of response.

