- 11.23 PROGRESSION (PD): Patients will receive protocol therapy unless they have evidence of disease progression according to the NCI criteria³ as evidenced by:
 - 11.231 ≥ 50% increase in the sum of the products of at least 2 lymph nodes on 2 consecutive determinations 2 weeks apart (at least one node must be ≥2 cm) or the appearance of new palpable lymph nodes >1.5 cm not due to a tumor flare. Enlargements or the appearance of new nodes due to a tumor flare do NOT qualify as progression.
 - $11.232 \ge 50\%$ increase in the size of the liver and/or spleen as determined by measurement below the respective costal margin on 2 consecutive determinations 2 weeks apart and with a minimum of $a \ge 2$ cm increase in size from baseline; or appearance of hepatomegaly or splenomegaly which was not previously present at baseline and not due to a tumor flare.

Protocol Version Date: November 25, 2014

- 11.233 Transformation to a more aggressive histology (e.g. Richter's transformation).
- $11.234 \ge 50\%$ increase in the absolute number of circulating lymphocytes NOT due to infection or tumor flare (taking as reference for progressive disease the smallest absolute lymphocyte count recorded since the treatment started). The absolute lymphocyte count must be at least $5000/\text{mm}^3$ to qualify as disease progression.
- 11.235 In the absence of progression as defined by 1, 2, 3, or 4 above, the presence of $a \ge 2$ g/dl decrease in HGB, or $\ge 50\%$ decrease in platelet count, or absolute neutrophil count will NOT exclude a patient from continuing the study. Work-up of such decreases to exclude auto-immune hemolytic anemia, pure red cell aplasia, or idiopathic thrombocytopenic purpura (ITP) should be considered.
- 11.236 For patients who achieve a CR or nodular PR, progression will be defined as recurrence of circulating leukemia cell clone and an ALC
 >5000 or recurrence of adenopathy >1.5 cm not due to a tumor flare.
- 11.24 STABLE DISEASE (SD): Patients who do not meet criteria for CR, CRi, nPR, CCR, PR, or PD will be classified as having "stable disease". The first formal response evaluation should occur no sooner than the end of cycle 2.
- 11.25 Not PD: The patient was evaluated for progression only this cycle and a formal response evaluation did not occur. The patient did not meet the criteria for progression per section 11.23.

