Note: Formal response evaluation should occur every 2 cycles during treatment, with the first response evaluation occurring at the end of cycle 2. Formal response evaluation should occur every cycle during observation. Objective status should be classified as PD vs. Not PD on cycles when a formal response evaluation does not occur.

11.3 EVALUATION OF MINIMAL RESIDUAL DISEASE (MRD): MRD will be assessed by flow cytometry and/or PCR for patients who achieve a CR/nPR/CRi. 43 MCCC Addendum 1

| | CCR ¹ | CR ² | CRi ³ | nPR ⁴ | PR ⁵ | PD ⁶ |
|---------------------------|--------------------------------------|--------------------------------------|------------------------------------|-------------------------------------|--|--|
| PHYSICAL EXAM | | | | | I | |
| Nodes ⁷ | None | None | None | None | ≥50% ↓ | \geq 50% \uparrow , new nodes |
| Liver/spleen ⁸ | Not palpable | Not palpable | Not palpable | Not palpable | ≥50% ↓ | \geq 50% \uparrow , newly palpable |
| Symptoms | None | None | None | None | N/A | Ñ/Â |
| PERIPHERAL BLOC | DD | | | · | | |
| ANC | >1500/µL | >1500/µL | See footnote 3 | >1500/µL | >1500/µL or >50% improvement from baseline | See footnote 6 |
| Platelets | >100,000/ µL | >100,000/µL | See footnote 3 | >100,000/µL | >100,00/µL or >50% improvement from baseline | See footnote 6 |
| Hemoglobin | >11.0 g/dL without transfusion | >11.0 g/dL without transfusion | See footnote 3 | >11.0 g/dL without transfusion | >11.0 g/dL or >50% improvement from baseline without transfusion | See footnote 6 |
| Lymphocytes | <4000/µL | <4000/µL | <4000/µL | <4000/µL | \geq 50% \checkmark | $\geq 50\% \uparrow$ to at least $5,000/\mu$ L |
| BONE MARROW | N/A | <30% lymphocytes; no nodules | <30% lymphocytes; no nodules | bone marrow nodules ⁴ | N/A | N/A |

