- 6. Progression: Fulfilling the criteria as noted in section 11.23. Prior to the formal response evaluation, baseline on study measurements will be used to determine disease progression (e.g. not cycle by cycle comparisons). Once patients undergo formal response evaluation, the nadir value at either baseline or time of response will be used for evaluating future disease progression. In the absence of other indices of clinical progression, the presence of a ≥2 g/dL decrease in hemoglobin or a ≥50% decrease in platelet count and/or absolute neutrophil count will not exclude a patient from continuing on the study. Although not mandatory, bone marrow aspirate and biopsy are strongly encouraged to better define the cause of the suppressed counts (i.e. treatment- versus disease-related).
- 7. Measurement of lymphadenopathy will be determined on physical exam by adding the sum of the products of the maximal perpendicular diameters of measured lesion(s). No simultaneous increase in the size of any lesions or the appearance of any new lesions may occur for more than 2 consecutive cycles. Minor fluctuations are acceptable as long as they don't exceed 50% of previous measurement. However, if they do exceed 50% of the previous measurement it should be held for 2 consecutive cycles to rule out the possibility of nodes that wax and wane. For purposes of determining CCR and nPR, all nodes on physical exam need to be ≤ 1.5 cm in maximal dimension or documented to be free of CLL by biopsy. NOTE: Information from CT scans regarding lymphadenopathy is not considered in the standard classification of response with the exception of the patients fitting criteria of section 11.218 and 11.228.
- 8. Measurement of hepatosplenomegaly will be determined by noting the maximal distance below the respective costal margins of palpable hepatosplenomegaly during rest (e.g., not during deep inspiration). NOTE: Information from CT scans regarding hepatosplenomegaly is not considered in the standard classification of response with the exception of the patients fitting criteria of section 11.218 and 11.228.

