 - 16.422 Time to Progression: Time to disease progression is defined as the time from registration to the earliest date of documentation of disease progression. If a patient dies without a documentation of disease progression the patient will be considered to have had tumor progression at the time of their death unless there is sufficient documented evidence to conclude no progression occurred prior to death. In the case of a patient starting treatment and then never returning for any evaluations, the patient will be censored for progression on day 1 post-registration. Patients who receive subsequent treatment for CLL before disease progression will be censored on the date of their last disease assessment prior to initiation of the subsequent treatment. The distribution of time to progression will be estimated using the method of Kaplan-Meier (Kaplan-Meier, 1958).⁶³
 - 16.423 Adverse Events: Platelets and hemoglobin will be graded according to the Grading Scale for Hematologic Adverse Events in CLL Studies in Appendix V. The maximum grade for each type of adverse event, regardless of causality, will be recorded and reported for each patient, and frequency tables will be reviewed to determine adverse event patterns. Adverse events will continue to be recorded and reported up to 30 days after the last day of study drug treatment.
- 16.43 Correlative Analyses: Due to the small overall sample size, the results of the following analyses will be considered exploratory and hypothesis-generating in nature.
 - 16.431 Immune cellular microenvironment: To determine the effect of lenalidomide on the immune effector arm, immune function will be evaluated before and during treatment by assessing T and NK cell quantification in both peripheral blood and bone marrow. Changes in these values over time will be both graphically and quantitatively summarized and explored. In addition, these values will be explored in

relation to response (responder vs non-responder as well as by quality of response, i.e. CR vs PR).

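### The liver/spleen progression rule uses baseline in 11.232 but the nadir in 11.1 and footnote 6, and 11.236 has no organ criterion after CR or nPR, so TTP can be lengthened

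*Combined protocol and SAP*

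**What the plan says.** All references are to the combined protocol and SAP.

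- **11.232, liver/spleen progression.** A rise of at least 50%, on two determinations two weeks apart, must include a minimum 2 cm gain measured from baseline. The alternative is "appearance of hepatomegaly or splenomegaly which was not previously present at baseline". The 50% test names no reference value. The other two tests name baseline.
- **11.1, schedule of evaluations.** After formal response evaluation, "the nadir value at either baseline or time of response evaluation will be used for evaluating future disease progression".
- **Footnote 6 of the response table (11.4).** "Prior to the formal response evaluation, baseline on study measurements will be used to determine disease progression". After that, "the nadir value at either baseline or time of response will be used for evaluating future disease progression".
- **Response table, PD column, liver/spleen row.** A rise of at least 50%, or "newly palpable", with no condition about baseline.
- **11.236.** "For patients who achieve a CR or nodular PR, progression will be defined as recurrence of circulating leukemia cell clone and an ALC" above 5000, or recurrent adenopathy above 1.5 cm not due to flare. Liver, spleen and transformation are not mentioned, and CRi and CCR are not named.
- **16.422.** "Time to disease progression is defined as the time from registration to the earliest date of documentation of disease progression". A patient who starts other CLL treatment before progression is censored at the last assessment before that treatment.
- **11.23 and 13.1.** Progression also ends protocol treatment.

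**The concern.** Two assessors can read the same spleen measurement differently. One uses 11.1 and the table and calls progression against the patient's best size. The other uses 11.232 as written and does not call it until the organ has passed its pretreatment size. The second reading is hard to dismiss as careless, because footnote 6 and 11.25 both send the reader back to 11.23 for the criteria.

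Section 11.236 adds a second gap. CR requires that liver and spleen are not enlarged on examination (11.212), so a returning spleen is a loss of CR. Yet the definition of progression written for CR and nodular PR does not list it.

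The endpoint at stake is time to progression, a stated secondary goal (2.22). Organ regrowth that goes unrecognised is dated late. If it leads to new CLL therapy first, 16.422 turns it into a censored observation instead of an event.

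**Working it through.** The plan gives no figure for this point, so there is none to reproduce. The check is a cross-reading, followed by the organ size at which the growth test is met.

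**Is the nadir rule enough to settle 11.232?** Not clearly.

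1. Section 11.1 uses baseline and nadir as different terms, so baseline in 11.232 cannot simply be read as nadir.
2. Where a criterion is meant to use the lowest value, the text says so: 11.234 takes the smallest lymphocyte count since treatment started. Section 11.232 says baseline twice.
3. The table drops the baseline condition that 11.232 imposes, so the table and the criterion it summarises differ.

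**Trigger size.** Let B be the baseline size and N the nadir, both in cm below the costal margin, with N no larger than B. Both the 50% rise and the 2 cm minimum must be met.

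- All tests from nadir: max(1.5N, N + 2)
- 50% from nadir, 2 cm from baseline: max(1.5N, B + 2)
- All tests from baseline: max(1.5B, B + 2)

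The sizes are assumed for illustration; the documents give none. For B = 10 and N = 4, a 60% reduction that meets the organ criterion for PR in 11.223:

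- all nadir: max(6, 6) = 6 cm
- mixed: max(6, 12) = 12 cm
- all baseline: max(15, 12) = 15 cm

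| Baseline | Nadir | All nadir | Mixed | All baseline |
|---|---|---|---|---|
| 10 | 4 | 6 | 12 | 15 |
| 8 | 8 | 12 | 12 | 12 |
| 8 | 4 | 6 | 10 | 12 |
| 8 | 2 | 4 | 10 | 12 |
| 4 | 0 | 2 | 6 | 6 |

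In the first row, progression is called at 6/4 = 1.5 times the nadir under the nadir rule, 12/4 = 3 times under the mixed reading, and 15/4 = 3.75 times on baseline alone. With no shrinkage (second row) the readings agree, so the discrepancy concerns only patients whose organ has shrunk. In the last row the organ became impalpable. The table's wording would then count its return as new; 11.232 would not, because it was present at baseline.

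**Direction.** Since N ≤ B, B + 2 is never below N + 2 and 1.5B is never below 1.5N. Both baseline-based thresholds are therefore at or above the nadir threshold for every pair of sizes. The literal wording can call organ progression later or not at all, never earlier.

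**Primary design.** The phase II rule (at least 5 of 14, then at least 15 of 37) does not use the progression definition. Exact binomial calculation gives stopping probabilities of 0.584 at a true rate of 0.30 and 0.090 at 0.50 (stated 0.58 and 0.09). The probabilities of declaring success are 0.095 and 0.853 (stated 0.10 and 0.85). The table in 16.32 reproduces and is untouched.

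**The case against.** The best reply is that 11.1 and footnote 6 already answer the question. They limit baseline to the period before the first formal evaluation and then set the nadir for progression in general. Footnote 6 is attached to the PD column, which includes liver and spleen. On that reading, organ regrowth in a partial responder can be progression.

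This stands in part. It rules out two stronger conclusions that a reader might draw: that 11.232 tests only against the pretreatment size, and that organ relapse cannot be called progression in such patients. Two places support calling it, the 50% test in 11.232 names no reference, and even on baseline wording sufficient growth beyond the pretreatment size counts. It does not remove the conflict, because 11.232 still states baseline for its other two tests.

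A second reply is that 11.236 is one more item in the 11.23 list and never says that it excludes the others. For transformation this is persuasive: 11.233 makes it progression without exempting responders, so the documents do not support inferring that transformation after CR is not progression. CRi and CCR, not being named, can likewise be read as remaining under 11.231-11.234. But 11.236 is phrased as the definition for CR and nodular PR, so its relation to the other items should be stated. If it adds to them, recurrent organomegaly falls back on 11.232 and its baseline condition.

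Third, other routes to progression remain: lymphocyte count from its lowest value, nodes, and generally death under 16.422. Time to progression is a descriptive Kaplan-Meier estimate with no planned test. This limits the consequence but does not remove it.

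**Conclusion.** The point holds as an internal contradiction with a known direction. Section 11.232 disagrees with 11.1, footnote 6 and the response table on the reference for liver and spleen, and 11.236 leaves recurrent organomegaly after CR or nodular PR unclassified. On the literal wording, regrowth in a responder with organomegaly at entry is not progression until it exceeds the pretreatment size: 12 to 15 cm instead of 6 cm in the assumed 10 cm to 4 cm case.

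Time to progression can therefore be lengthened. A reader might go further and say that it is overstated. The documents do not show that: they give neither the share of patients with palpable organs at entry, nor a rate of relapse confined to liver or spleen, nor an expected time to progression. The effect arises only for relapses of that kind that fall between the thresholds and are read under the baseline wording. The primary response-rate design is unaffected. The discrepancy should still be corrected, because it sits in an endpoint definition.

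**What to change.** 1. Reconcile 11.232, 11.1, footnote 6 and the response table on one reference value for the time-to-progression endpoint, covering the 50% test, the 2 cm minimum and the new-organomegaly condition. Sections 11.1 and footnote 6 already state the nadir.
2. State in 11.236 whether it adds to or replaces 11.231-11.234.
3. State how recurrent organomegaly and transformation after CR or nodular PR are classified, and which rule covers CRi and CCR.
4. Because progression also ends treatment (11.23, 13.1), the sponsor must reconcile those passages in the same amendment. This review takes no position on the treatment rule.

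The cost is wording only: liver and spleen are already measured on physical examination (4.0, note 2). Time to progression may become slightly less favourable.

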11.4 Summary Definition of objective response for patients with B-CLL

1. Clinical complete response (CCR) requires fulfillment of all physical exam and peripheral blood criteria as noted in the table above. No bone marrow biopsy is required to call a patient a CCR; however, patients who achieve a CR/nPR/CRi should have a bone marrow within one month of the formal response evaluation where clinical and laboratory evidence of complete response was first seen as instructed in the test schedule to confirm CR.

2. Complete response (CR) requires fulfillment of all physical exam and peripheral blood criteria for a duration of ≥2 months. A bone marrow aspirate and biopsy are required to document the response as a complete within one month of the formal response evaluation where clinical and laboratory evidence of complete response was first seen (see Section 11.21).

3. Patients who fulfill all criteria for a CR but who have a persistent anemia, thrombocytopenia, or neutropenia related to drug toxicity rather than residual CLL will be classified as CR with incomplete marrow recovery (CRi).

4. Nodular partial response (nPR) is essentially a patient in who it appeared that CR had been obtained but nodules are present in the bone marrow. It requires fulfillment of all physical exam and peripheral blood criteria for CR; however, when the bone marrow is done to confirm CR, nodules of malignant lymphocytes are found. See Section 11.215 regarding the distinction between clonal and regenerative nodules.

 Partial response (PR) requires fulfillment of at least two of the above-noted decrease in circulating lymphocytes, regression in adenopathy and regression in hepatosplenomegaly, and at least one other parameter listed above for a duration of ≥ 2 months. See Section 11 22.

Footnotes continued on next page.

MC128A

MC128A 44 MCCC Addendum 1

- 6. Progression: Fulfilling the criteria as noted in section 11.23. Prior to the formal response evaluation, baseline on study measurements will be used to determine disease progression (e.g. not cycle by cycle comparisons). Once patients undergo formal response evaluation, the nadir value at either baseline or time of response will be used for evaluating future disease progression. In the absence of other indices of clinical progression, the presence of a ≥2 g/dL decrease in hemoglobin or a ≥50% decrease in platelet count and/or absolute neutrophil count will not exclude a patient from continuing on the study. Although not mandatory, bone marrow aspirate and biopsy are strongly encouraged to better define the cause of the suppressed counts (i.e. treatment- versus disease-related).
- 7. Measurement of lymphadenopathy will be determined on physical exam by adding the sum of the products of the maximal perpendicular diameters of measured lesion(s). No simultaneous increase in the size of any lesions or the appearance of any new lesions may occur for more than 2 consecutive cycles. Minor fluctuations are acceptable as long as they don't exceed 50% of previous measurement. However, if they do exceed 50% of the previous measurement it should be held for 2 consecutive cycles to rule out the possibility of nodes that wax and wane. For purposes of determining CCR and nPR, all nodes on physical exam need to be ≤ 1.5 cm in maximal dimension or documented to be free of CLL by biopsy. NOTE: Information from CT scans regarding lymphadenopathy is not considered in the standard classification of response with the exception of the patients fitting criteria of section 11.218 and 11.228.
- 8. Measurement of hepatosplenomegaly will be determined by noting the maximal distance below the respective costal margins of palpable hepatosplenomegaly during rest (e.g., not during deep inspiration). NOTE: Information from CT scans regarding hepatosplenomegaly is not considered in the standard classification of response with the exception of the patients fitting criteria of section 11.218 and 11.228.

12.0 Descriptive Factors

- 12.1 Rai Stage: 0 vs. 1 vs. 2 vs. 3 vs. 4. (Appendix II)
- 12.2 $CD38^+$ expression: Positive ($\geq 30\%$) vs. negative (< 30%).
- 12.3 Chromosomal anomalies as detected by FISH: 13q- vs. 12+ vs. 11q- vs. 17p- vs. other abnormality vs. normal karyotype.
- 12.4 IgV_H mutation status: Mutated ($\geq 2\%$) vs. unmutated ($\leq 2\%$) vs. indeterminate.
- 12.5 ZAP-70 expression: Positive ($\geq 20\%$) vs. negative ($\leq 20\%$).
- 12.6 Dose level (to be assigned by the Registration Office): -2 vs. -1 vs. 1 vs. 2 vs. 3 .vs. 4.

13.0 Treatment/Follow-up Decision at Evaluation of Patient

- 13.1 If the patient develops PD at any time during active treatment, unacceptable adverse events, or patient refuses all further study participation, study treatment will be discontinued and the patient will go directly to event monitoring. Patients will then be followed in event monitoring per Section 18.0.
- 13.2 Patients not progressing on active treatment will continue treatment per protocol up to a maximum of 12 cycles. After the completion of 12 cycles, the patient will go to observation (maximum duration of observation 2 years).
- 13.3 Phase I Only: If a patient fails to complete the first two cycles of treatment for reasons other than toxicity, the patient will be regarded as inevaluable and will be replaced.
- 13.4 A patient is deemed ineligible if after registration, it is determined that at the time of registration, the patient did not satisfy each and every eligibility criteria for study entry. The patient may continue treatment off-protocol at the discretion of the physician as long as there are no safety concerns, and the patient was properly registered. The patient will go directly to the event-monitoring phase of the study (or off study, if applicable).
 - If the patient received treatment, all data up until the point of confirmation of ineligibility must be submitted. Event monitoring will be required per Section 18.0 of the protocol.
 - If the patient never received treatment, on-study material and the End of Active Treatment/Cancel Notification Form must be submitted. No further data submission is necessary.
- 13.5 A patient is deemed a *major violation*, if protocol requirements regarding treatment in cycle 1 of the initial therapy are severely violated that evaluability for primary end point is questionable. All data up until the point of confirmation of a major violation must be submitted. The patient will go directly to the event-monitoring phase of the study. The patient may continue treatment off-protocol at the discretion of the physician as long as there are no safety concerns, and the patient was properly registered. Event monitoring will be required per Section 18.0 of the protocol.

13.6 A patient is deemed a *cancel* if he/she is removed from the study for any reason before any study treatment is given. On-study material and the End of Active Treatment/Cancel Notification Form must be submitted. No further data submission is necessary.

